### **Consent Process:**

**a. Approaching the patient and family:** The CSC will screen admissions each weekday and will only approach potential study participants after confirming eligibility (e.g. “surprise question”) and getting approval from the treating clinician.

**b. CAG and CSC meet with patient and family:** Following approval, the CSC will contact the CAG member “on-call” for the day to speak with the patient. The CAG member and CSC will approach the patient. The CAG member will introduce themselves and the CSC, and describe the study to the patient. The CAG will emphasize their role in developing the study and how this study was designed to help the community. If the patient indicates that he/she would like to participate, the CSC will provide an overview of the study, including a description of palliative care, the tele-consult equipment and process, (if randomized to that group), and randomization using a simple visual diagram. (These materials were developed by the R21 CAG and will be reviewed and adapted by each hospital-specific CAG). The CSC will then read the consent form to all patients (assuming no or limited literacy) unless the patient prefers to read it themselves. The family member is invited to participate and will sign a separate consent agreeing to complete questionnaires regardless of group assignment. The CSC will assist the patient (and separately the family member) to complete the baseline questionnaires using an electronic tablet that connects directly to the REDCap database. Baseline data are collected prior to randomization, so study coordinator blinding is not necessary.

The CSC will screen, obtain consent and organize the tele-consult. The CSCs will remain in daily contact with hospital staff and participate in team meetings to remind clinicians about eligibility criteria. Team meeting attendance will allow the CSC to clarify the study goals and protocol and to strategize solutions if challenges arise. The BSC will collect all data following patient randomization.

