Within 24 hours of conducting the Tele-consult, the remote palliative physician will seek an interdisciplinary team review, develop the plan, and make recommendations, which may include immediate patient care (e.g., symptom relief) and continuing care, related to the hospital stay and following discharge. Recommendations may also include referrals to other supportive resources such as a hospital social worker or pastor. The written consult will be documented using a standardized note template that corresponds to the 8 NCP palliative care domains and will be provided via a secure HIPAA-compliant portal that will be part of the patients' inpatient medical record. As needed, verbal contact will also occur between the palliative care physician and the hospitalist staff.

**Contact #2** Day 3 (approximately 24-48 hours after first contact). The CSC will arrange a follow up videoconference between the remote palliative care physician and patient if in hospital or via phone if the patient has been discharged. The purpose of this second contact is to determine how patient is progressing, if the plan was implemented, if hospital staff/patient has encountered any challenges or questions, and to determine who will be assuming the patient's care in the community. Documentation of the contact will be provided as described above.

**Contact #3** Day 6 (post consult) (via videoconference if patient is in hospital, via phone if discharged.) To determine if patient is experiencing new or ongoing challenges, to confirm availability of community or hospice care as appropriate.

**Tele-consult Intervention + Usual Care.** In the usual care group and the intervention group, a study coordinator at each site will administer questionnaires to the patient and their designated family/friend caregiver, in person or telephone (if patients are discharged during the study period) at baseline (T1), Day 7 (T2) and Day 30 after hospital discharge (T3). (Study coordinators administering T2/T3 assessments will be blinded to study group- aka Blinded Study Coordinators [BSC]).

Table 5. Measures and Data Collection Schedule						
Construct	Instrument & Description	# of Items	T1 Baseline	T2 Day 7	T3 Day 30	
Demographics	Demographic Questionnaire- Age, gender, race/ethnicity, marital status, religion, education, occupation, insurance status, financial status.	10	X			
Primary Aim						
Symptom Burden	Edmonton Symptom Assessment Scale (ESAS) - symptom intensity using visual analog	9	X	X		

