Secondary Aims						
Patient and Caregiver QoL	PROMIS Global Health -10. Evaluates physical, social, and emotional health in healthy & chronically ill adults	10	X	X		
Family Satisfaction with Care	FamCare - family satisfaction with availability of care, physical & psychosocial care, information giving	20	X	X		
Patient Satisfaction with Care	Feeling Heard and Understood - Self-report quality measures for palliative care settings on Likert scale (1 item)	1	X	X		
Caregiver Burden	Montgomery Borgatta Caregiver Burden Scale (MBCB)-subscales objective, subjective, demand burden	14	X	X		
Resource Use	Hospital admission, ED visit, hospice	NA			X	
Exploratory Aim						
Mediators	Consult recommendations implemented by Hospitalist & Pt	NA		X		

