### **a. Spreadsheets**

Each CSC and BSC will maintain a number of spreadsheets and documents to track all aspects of data collection at their respective sites.

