#### **Referral spreadsheet**

One spreadsheet should track potential patient referrals. No identifiable information should be included in the spreadsheet. The spreadsheet should include the following:

- Referral number (e.g., 'referral 001')
- Date of referral
- Name and title of person making referral (e.g., 'Nora, nurse')
- Patient age, ethnicity, sex
- Patient diagnosis
- Name of treating clinician
- Whether or not treating clinician's permission was granted
  - If no, why not?
  - Date of treating clinician's permission/denial
- Whether or not patient enrolled'
  - If no, why not?
  - Date of patient's enrollment/non-enrollment
  - If yes, patient UID

**UID spreadsheet/linkage log.** The linkage log will be the only spreadsheet that contains PHI/identifiable patient information. It will contain the patient's UID, patient's name, caregiver's name, and phone numbers. This spreadsheet should be password encrypted, and shared only with members of the study team.

**Implementation of PC recommendations spreadsheet.** The PC recommendations and implementation spreadsheet will track each patient consult using the patient UID. It will contain a list of each of the PC recommendations, and whether or not each of the recommendations was implemented by the treating clinician(s).

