**c. Data collection sheet**

The CSC will fill out a data collection sheet for each patient (both Group A and Group B), using patient's UID. The data collection sheet will record:

- Demographics
- Diagnosis
- Readmissions
- Study group
- PC recommendations
- Family implementation of PC recommendations (determined via family interview)

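### The plan contradicts itself on who collects the Day 7 consult-implementation item, so blinding of the primary-outcome assessor is not protected

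*Combined protocol and SAP*

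**What the plan says.** Table 5 in section X lists two things under T2, Day 7, that matter here. One is the primary outcome, "Edmonton Symptom Assessment Scale (ESAS) - symptom intensity using visual analog". The other, under the exploratory aim, is the mediator "Consult recommendations implemented by Hospitalist & Pt".

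On who collects what, the text gives several rules:

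- Section IX, Consent Process: "The BSC will collect all data following patient randomization".
- Section X, before Table 5: "Study coordinators administering T2/T3 assessments will be blinded to study group".
- Section XII, a. Spreadsheets: "Each CSC and BSC will maintain a number of spreadsheets and documents to track all aspects of data collection at their respective sites".
- Section XII, implementation spreadsheet: "The PC recommendations and implementation spreadsheet will track each patient consult using the patient UID". It covers implementation by treating clinicians, and no coordinator is named as its owner.
- Section XII, c. Data collection sheet: the CSC completes a sheet for every patient in both groups. Its entries include the study group, the recommendations, and "Family implementation of PC recommendations (determined via family interview".

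The opening of section XII also has both coordinators send all study documents to the statistician, fidelity checklists and data collection sheets among them.

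**The concern.** A tele-consult, and so any recommendation from it, exists only in the intervention arm. Anyone who asks about implementation, or opens a record of it, learns the patient's assignment. Absence of the item where it is otherwise routine is just as informative.

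Patients and caregivers know their assignment. The ESAS is self-reported and is taken by a coordinator in person or by telephone. Interviewer blinding is therefore the plan's main protection against prompting or recording answers differently by arm. The Day 7 quality of life, satisfaction and caregiver burden measures are collected at the same time point and share the exposure. The plan includes no record of whether the assessor learned the arm, and section XI has no analysis that addresses it, so a breach could go unnoticed.

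**Working it through.** No arithmetic applies: the point rests on who handles which record, and the plan states no figure for it. The check is to set the rules side by side.

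1. **Does the item reveal the arm?** Yes. Section IV gives the consult to the intervention group only, on top of usual care.
2. **When is it due?** At T2, in the same column of Table 5 as the ESAS.
3. **Who collects it under the general rules?** Section IX gives the BSC everything after randomization, with no exception. Section X makes the T2 assessor the BSC. Applied to the Table 5 row, these two rules give the item to the BSC.
4. **Who collects it under the specific rules?** Section XII c has the CSC record the recommendations and interview the family about them. Section XII b gives the CSC the fidelity checklist. These are also post-randomization data, so they conflict with the section IX rule. Nothing says which text governs.
5. **What is left unassigned?** The clinician part of the mediator sits on the implementation spreadsheet, which has no named owner, under a heading that has both coordinators maintain spreadsheets.
6. **Is access restricted?** No text bars the BSC from the implementation spreadsheet, the fidelity checklist (which exists only where there was a consult) or the data collection sheet (which states the study group). Both coordinators transmit such documents.
7. **Could exposure come before the ESAS?** Yes. Recommendations are due within 24 hours of the tele-consult, so the records can exist well before Day 7. If the BSC met the item only during the T2 interview, the effect on the ESAS would depend on the order of questions, which is not stated. If the arm were learned after the ESAS, only the remaining Day 7 measures and T3 could be affected.

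Steps 3 and 4 give different collectors for overlapping content, step 5 leaves a gap, and step 6 shows that nothing contains the consequence.

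**The case against.** The strongest reply is that the plan's intent is clear and its most specific text is right. No sentence names the BSC for the mediator or its spreadsheet. The CSC organizes the consult, is in the room, completes the fidelity checklist and holds the sheet with study group and recommendations. Section X describes the T2/T3 task as giving questionnaires. Table 5 enters NA for the mediator's number of items, so it may not be an interview item at all. The spreadsheet sentence does not say that each coordinator opens every file. On this reading, the section IX rule is loosely worded and means questionnaire outcomes.

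Much of this stands. A reader might infer that any site following the plan will unblind its ESAS assessor. The documents do not support that: a site that follows section XII c keeps the family part with the CSC, and the order of Day 7 questions is open. Nor is the instruction to participants not to disclose their group the only safeguard. Section VII also routes the assignment through the coordinating site to one local unblinded coordinator and says the rest of the team stays blind.

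What does not stand is that intent settles the matter. The section IX rule is unqualified and is the one staff would consult about post-randomization data. The NA entry does not remove the item from T2, and a non-questionnaire record reveals the arm just as well. Section VII states who should stay blind but does not keep arm-revealing files from the BSC.

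**Conclusion.** The point holds as a contradiction with a gap in protection. Sections IX and X with Table 5, read literally, give a consult-only item to the blinded assessor of the primary outcome. Section XII c gives overlapping content to the CSC, and the clinician-implementation spreadsheet belongs to no one. A site that follows section IX literally, or lets the BSC handle these records, could unblind the assessor of the ESAS and the Day 7 secondary outcomes.

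The documents do not allow the size of any bias to be estimated. It would depend on how many sites took the literal reading, whether the arm was learned before the ESAS, and how far knowing it changed the interview. None of these is given. Importance and confidence are both moderate: the wording conflict is plain, but whether it would break the blind in practice depends on how sites resolve it. The conclusion assumes that the CSC is the unblinded local coordinator of section VII, which the CSC's duties imply.

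**What to change.** - **Section IX:** narrow the rule so that the BSC collects all T2/T3 questionnaire outcomes and the CSC collects intervention-delivery data. The same sentence should say who records resource use at T3, which fits neither category; readmissions now sit on the CSC's sheet.
- **Table 5 and section XII:** assign the mediator item, the implementation spreadsheet, the fidelity checklist and the family-implementation interview to the CSC only. Hold the interview after the BSC has completed the T2 questionnaires.
- **Access:** set REDCap and file permissions so that the BSC cannot open, maintain or transmit any record showing study group, recommendations or implementation.
- **Day 7 procedure:** have the BSC give the ESAS first and record whether the arm was revealed.

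Both coordinator roles already exist at each site, so no new staff are needed. The cost is protocol wording, a permissions change and one extra field. The small downside is one short CSC contact timed after T2 in intervention patients. Section XII c already plans that interview but does not state when it takes place.

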## **XI. Statistical Analysis Plan**

Demographic variables (e.g., age, sex, race, disease) will be summarized and compared across treatment groups using t-tests and nonparametric Wilcoxon signed rank tests for continuous measures (age), binomial tests (sex, race), and chi-square statistics for categorical variables (e.g., marital status, education). All demographics and stratification variables found to differ across treatment groups will be included in regression models (referred to as the vector  $ZZ_{ii}$  in the regression models to follow); however, race will be included in the final models separately from the vector  $ZZ_{ii}$  vector. Tabulations of binary and categorical variables will be presented for all measures and broken down by treatment group. Age will be summarized by mean and standard deviation for all participants, and broken down by treatment group.

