#### IV. Study Design

This study consists of 2 phases:

**Phase I Convening & Soliciting CAG Participation in study design.** This phase will consist of assembling CAG members to review study procedures and some CAG members will be trained to approach potential study participants. Potential CAG members (8, with equal numbers of AA and W) will be identified by the hospital staff and community leaders of each of the three sites, and invited to participate in the CAG. Potential CAG members will include respected members of the community, those who have recently lost a loved one and understand end of life care, and community leaders. Potential members will be discussed by the recruiters with the study PIs to ensure there is socio-demographic balance, and equal representation of African American and

White members, to ensure all will feel comfortable participating and contributing, and to ensure that they are not all from the same family/church/social group. Following this step, a formal written invitation will be extended to those selected, followed by a phone call by the Study Manager.

**Phase II Conducting the RCT.** In Phase II, we will conduct a randomized controlled trial (RCT) at the 3 sites to test the effectiveness of this innovative program. We will recruit 352 hospitalized AA and W adults over age 65 whose treating physician would not be surprised if they died within the next year and the patients' family/friend caregiver. Half of the patient participants (N=176) will be randomized to receive usual care appropriate to their illness. Patients randomized to usual care in each of the three participating hospitals will receive inpatient care appropriate to their illness. This includes assessment and treatment by the admitting physician, along with any subspecialists that are consulted. The formulation and sharing of prognostic information and the engagement of patients and families in establishing goals of care will be according to the standards of the admitting physician and subspecialists. Treating clinicians may include hospitalists, nurse practitioners, social workers, pastoral care, and occasionally, the patient's primary care practitioners who have hospital privileges.

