The other half of the patient participants (N=176) will receive the culturally-based palliative care consult. Patients in the intervention group will receive usual care as described above, and, in addition, will participate in a standardized, comprehensive palliative care Tele-consult

assessment as well as a follow up by the palliative care physician on Day 3 and 6 following the initial consult.

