## **VII. Randomization Plan**

The randomization scheme will be executed via REDCap, a clinical trials management software program. Participants will be randomly assigned to group (1:1) using a computer-generated program overseen by [name]. The randomization scheme will be stratified by site (SC, AL, MS) race (W, AA), and illness trajectory. As the Central Coordinating Site, UAB will manage the randomization process. The UAB study manager will be alerted to the assignment by REDCap and will trigger the local unblinded study coordinator to communicate assignment to the participant and initiate study protocol. All other members of the research team will remain blind to group assignment and participants will be instructed not to discuss their assignment with the local study coordinator collecting the outcome assessments.

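### A paired test is named for comparing age between independent arms; more importantly, the covariate rule it feeds will tend to leave site and illness trajectory out of the models

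*Combined protocol and SAP*

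**What the plan says.** Section XI (Statistical Analysis Plan) states that demographic variables will be "compared across treatment groups using t-tests and nonparametric Wilcoxon signed rank tests for continuous measures (age"). It assigns one kind of test to sex and race, and chi-square to categorical variables.

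The results then have a use: "All demographics and stratification variables found to differ across treatment groups will be included in regression models". There is one exception: "race will be included in the final models separately from the vector" that holds the selected covariates. The section also plans a descriptive summary: "Age will be summarized by mean and standard deviation for all participants, and broken down by treatment group".

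On design, section IV says "Half of the patient participants (N=176) will be randomized to receive usual care appropriate to their illness" and "The other half of the patient participants (N=176) will receive the culturally-based palliative care consult". Section VII says "Participants will be randomly assigned to group (1:1) using a computer-generated program" and "The randomization scheme will be stratified by site (SC, AL, MS) race (W, AA), and illness trajectory". Table 5 in section X schedules the demographic questionnaire, which includes age, at baseline (T1) only.

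**The concern.** There are two linked problems.

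**The test name.** The signed-rank test works on differences within pairs. Nothing in the plan pairs a patient in one arm with a patient in the other: allocation is individual, and stratification is not matching. Age is recorded once, so there is no within-patient pair either. As written, the test does not fit the comparison.

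**The rule it feeds.** The baseline comparisons decide which covariates enter the regression models. For age, two tests are listed and nothing says which one governs. For every variable, the supplied text gives no threshold for calling the arms different. The rule also covers the stratification variables, and stratified randomisation exists to make those alike between arms. A rule that adjusts only for factors that differ will therefore tend to omit the factors used in randomisation. If site or illness trajectory predicts symptom burden, a model without it leaves in the residual some variation that the stratified allocation has already removed from the treatment comparison. The standard error is then larger than it need be. The documents do not give the strength of that association, so this loss cannot be sized here.

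**Working it through.** The plan states no figure to reproduce on this point. The one arithmetic check on the arms agrees: 352 / 2 = 176.

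**Inputs from the documents:** 176 per arm, 1:1 individual allocation, strata of site (3), race (2) and illness trajectory.

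**Assumptions not in the documents:** no true age difference between arms; 352 complete ages; permuted blocks of 2, 4 or 6 within strata; sites split 50/25/25; illness trajectory taken as the three illness paradigms of section VI, giving 3 × 2 × 3 = 18 strata; a cut-off of 0.05 unless stated. Four age distributions were tried: normal (mean 75, SD 7), the same truncated at 65, 66 + gamma (shape 2, scale 4.5) and 66 + exponential (mean 8), with 12,000 simulated trials each.

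**Step 1. Can the named test be run?** Only if the arms are exactly equal and patients are paired arbitrarily. With arms of 170 and 182 it cannot be computed. With 176 per arm, its result depends on row order. In one simulated dataset, 2,000 re-orderings of one arm moved the signed-rank p-value between 0.030 and 0.498. The rank-sum p-value stayed at 0.060 and the t-test p-value at 0.162.

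**Step 2. How often would the wrong name change the decision on age?**
- Chance of exactly equal arms: 0.272, 0.203 and 0.169 for block sizes 2, 4 and 6 (20,000 simulations).
- Signed-rank and rank-sum disagree in 2.04% to 3.23% of trials, depending on the age distribution.
- Joint chance = P(equal arms) × P(disagree). Lowest: 0.169 × 0.0204 = 0.34%. Highest: 0.272 × 0.0323 = 0.88%.

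**Step 3. How much does the missing precedence matter for age?** The two valid tests, t and rank-sum, disagree in this share of trials:

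| Age distribution | t vs rank-sum disagree |
|---|---|
| Normal | 1.97% |
| Normal, truncated at 65 | 1.64% |
| 66 + gamma | 3.79% |
| 66 + exponential | 4.71% |

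**Step 4. How much does the missing threshold matter for age?** With no true difference, the tests select age in 4.7% to 5.2% of trials at 0.05, 9.6% to 10.2% at 0.10 and 19.3% to 20.6% at 0.20. This is what a significance level means. It shows only that the unstated threshold sets how often chance puts age in the model.

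**Step 5. What does the rule do with the stratification factors?** With permuted blocks, a stratum can be out of balance by at most half a block, which is 3 patients at block size 6. In 5,000 simulated trials for each block size, chi-square tests selected site, race and illness group in 0 trials at 0.05, 0.10 and 0.20 alike. Race enters the final models regardless. Site and illness trajectory have no such protection.

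**The case against.** The sentence speaks of comparing treatment groups, so the intended two-sample comparison is clear and the wrong name is a slip. A valid t-test stands beside it, and no statistician is likely to pair unrelated patients arbitrarily. This stands: the test name alone is close to harmless.

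It would be too strong to say that no test governs any variable. Sex and race have one kind of test and categorical variables have another. Only age has two without precedence. The missing threshold does apply to all variables, with a limit: section XI points ahead to regression models that do not appear in the supplied text, and some pages were removed before review. A threshold could be stated there. The contents list puts sections XI and XII on the same page, which suggests a short section but does not settle the matter.

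A reader might also infer that the primary ESAS comparison is invalid or biased. The documents do not support that. Omitting a balanced factor costs precision if the factor is prognostic; nothing here shows bias or a changed result. Nor is race at risk of omission.

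Finally, block sizes, site split, illness groups and age distributions are assumed. Section VII does specify stratification, however, and near balance on the strata is its purpose. The direction of Step 5 does not depend on the exact block size.

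**Conclusion.** The point holds and is minor. The signed-rank test is the wrong test for two independent arms, and nothing in the supplied text corrects it. Its own effect is below 1% of trials on the decision about age (0.34% to 0.88%, under the assumptions listed). The covariate rule is the more consequential part: under stratified randomisation with permuted blocks it will rarely, if ever, select site or illness trajectory, so the models would omit two of the three factors used in randomisation. Confidence is high on the test name and on how the rule treats balanced strata. It is lower on the absence of a threshold, because the models that section XI announces are not in the supplied text.

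**What to change.** In section XI:

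1. Replace the signed-rank test with the Wilcoxon rank-sum (Mann-Whitney) test.
2. Keep baseline comparisons descriptive, so that they select no covariates.
3. State that every regression model includes site, race, illness trajectory and age, whatever the baseline comparisons show.

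If the sponsor keeps the selection rule for other demographics, it should give one governing test and one threshold for each.

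The cost is a phrase and a sentence or two. The data are already collected and the sample size does not change. The price is a few model degrees of freedom: site 2 + race 1 + illness trajectory 2 (if three groups) + age 1 = 6. Race is already planned, so 6 − 1 = 5 are new, against 352 patients.

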### Recruitment Estimates by Hospital

Participating Hospital	no. beds	Annual Admissions	Observed Eligible Patients* (annualized)	Estimated Annual Consults**	Annual recruitment assuming 50% refusal (range of observed - estimated)
Aiken Hospital, SC	243	3767	264	188	132-94
Russell Hospital, AL	80	1506	240	109	54
Highland Hospital, MS	33	1200	296	51	148-25

\*Hospitals estimated eligible patients based on study eligibility criteria  
\*\*CAPC estimates of consults based on 5-7% of annual admissions

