### VI. Inclusion and Exclusion Criteria

#### Patient Inclusion Criteria:

- (1) AA or W;
- (2) > 65 years old; has a condition which fits into one of 3 illness paradigms (including: cancer, cardiac disease, pulmonary disease, neuro-degenerative disease, renal disease, stroke, sepsis, hepatic disease)
- (3) Clinician answers “no” to question: “Would you be surprised if this person died in the next 12 months?”
- (4) Patient has a caregiver who has been involved in their care.
- (5) Able to complete baseline interviews.

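### Site and illness trajectory enter the models only if the arms differ on them, so two of the three stratification factors are in effect left out; baseline ESAS adjustment is unspecified

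*Combined protocol and SAP*

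**What the plan says.** Section VII (Randomization Plan) states: "The randomization scheme will be stratified by site (SC, AL, MS) race (W, AA), and illness trajectory". Allocation is 1:1. Block size is not given, and the levels of illness trajectory are not listed there. The patient inclusion criteria in Section VI require that the patient "has a condition which fits into one of 3 illness paradigms", which suggests three levels.

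Section XI (Statistical Analysis Plan) compares baseline variables between arms and then sets the covariate rule: "All demographics and stratification variables found to differ across treatment groups will be included in regression models". These variables form a vector Z. There is one exception: "however, race will be included in the final models separately from the vector". No threshold is given for deciding that a variable differs. The section points forward to regression models, but none appears in the text.

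Table 5 in Section X schedules the primary outcome, "Edmonton Symptom Assessment Scale (ESAS) - symptom intensity using visual analog", at baseline (T1) and Day 7 (T2). Section IX says baseline data are collected before randomisation. Nothing in the text says whether the baseline score is a covariate, or whether change from baseline is analysed.

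**The concern.** Stratification makes the arms alike on site, race and trajectory. The rule then requires the arms to be unlike on site or trajectory before the model may use them, so the two steps work against each other.

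The sentence can be read in two ways. If the condition governs both demographics and stratification variables, which is the natural reading, demographics enter when they differ by chance, whether or not they predict symptoms. If it governs only the stratification variables, all demographics enter. Site and trajectory are conditional either way.

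Two things are at stake. First, when allocation is balanced on prognostic factors that the model omits, the model reports a standard error that is too large, so the interval is too wide and the test is conservative. Second, the covariate set is not fixed until baseline data split by arm have been examined against an unstated threshold.

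Baseline ESAS is a separate matter. It is neither a demographic nor a stratification variable, so this rule cannot admit it.

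**Working it through.** **Inputs from the document.** N = 352, 176 per arm (Section IV); 1:1 allocation stratified by site (3), race (2) and illness trajectory (Section VII); three illness paradigms (Section VI), giving 3 × 2 × 3 = 18 strata if these are the trajectory levels; site shares from the recruitment table in Section IV (94/54/25 or 132/54/148); and the questionnaire items in Table 5.

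**Assumed, because the document does not give them.** Permuted blocks within strata; a chi-square test at 0.05 as the criterion for a difference; two-sided alpha 0.05; an effect of 0.30 SD; all 352 analysed; race 1:1 and equal trajectory levels; and the shares of variance explained. The plan's sample size cannot be reproduced without these. For orientation, 0.30 SD at 80% power needs 175 per arm, so it is a reasonable effect to illustrate with.

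**Step 1: how often would site or trajectory be flagged?** Simulation used 3,000 trials for each of 3 block sizes (4, 6, 8) and 2 sets of site shares, with 2 factors tested: 3,000 × 3 × 2 × 2 = 36,000 tests.

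- 18 strata: 0 of 36,000 flagged.
- 48 strata (8 trajectory levels): 4 of 36,000 flagged.
- No blocking: 128 to 166 of 3,000 per factor, or 4.3% to 5.5%, so each is still omitted about 95% of the time.

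A further simulation with other site and illness shares and blocks of 2, 4, 6 or 8 (4,000 trials each) also flagged none.

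**Step 2: the effect of omitting them under blocking.** Let R² be the share of ESAS variance that site and trajectory explain. In SD units the race-only model reports SE = 2/√352 = 0.1066, while the true SE is 0.1066 × √(1 − R²). Then:

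- interval ratio = 1/√(1 − R²)
- actual type I error = 2[1 − Φ(1.96/√(1 − R²))]
- power, race only ≈ Φ[(0.30/0.1066 − 1.967)/√(1 − R²)]
- power, always adjusted ≈ Φ[0.30/(0.1066√(1 − R²)) − 1.967]

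The powers below are from the noncentral t. The normal forms above agree to about 0.1 point.

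| R² (assumed) | Interval too wide by | Actual type I | Power, race only | Power, always adjusted | Gain (points) |
|---|---|---|---|---|---|
| 5% | 2.6% | 4.4% | 80.7% | 82.1% | 1.4 |
| 10% | 5.4% | 3.9% | 81.4% | 84.1% | 2.7 |
| 20% | 11.8% | 2.8% | 82.8% | 88.1% | 5.3 |

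Simulation (6,000 trials per setting, blocks of 4, 18 strata) agrees. For the three R² values, type I error was 0.044, 0.038 and 0.030 with race only, against 0.050, 0.048 and 0.051 with adjustment. Power was 0.808, 0.811 and 0.827 against 0.820, 0.838 and 0.883. These conservative-test figures need blocking and do not apply to unrestricted allocation.

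**Step 3: demographics admitted by chance.** Table 5 lists "Age, gender, race/ethnicity, marital status, religion, education, occupation, insurance status, financial status", which is 8 items without race. With independent 0.05 tests, the chance that at least one is flagged is 1 − 0.95⁸ = 0.337. Adding disease, which Section XI counts among the demographics, gives 1 − 0.95⁹ = 0.370. This costs little precision.

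**Step 4: baseline ESAS, separately.** For baseline-to-Day 7 correlation r, the SE is multiplied by √(1 − r²) with baseline as a covariate and by √(2(1 − r)) for a change score. A Day 7 model without baseline has power 80.1% at 0.30 SD.

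| r (assumed) | Baseline as covariate | Change score |
|---|---|---|
| 0.3 | 83.7% | 66.0% |
| 0.5 | 90.0% | 80.1% |
| 0.7 | 97.6% | 95.2% |

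**The case against.** The strongest reply is that the announced models are not in the text. Race shows that a stratification factor can sit outside Z, and the missing equations might carry a site term too. That caution is fair, and it is why baseline ESAS is called unspecified. It carries less weight for site and trajectory, because the visible rule addresses stratification variables directly and exempts only race.

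Second, Section XI lists disease among the demographics. If all demographics enter, disease would carry much of what trajectory predicts, leaving mainly site unadjusted. This stands: on that reading the R² values for site and trajectory together overstate the loss. It does not help on the natural reading, and it does nothing for site.

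Third, nothing in the document makes 5% a floor for R². At 1% and 2% the test runs at 4.9% and 4.8%, the interval is 0.5% and 1.0% too wide, and the power gain is about 0.3 and 0.5 points. This also stands: the strata effect may be very small.

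Fourth, the larger gains belong to baseline ESAS alone, and they are nil if the absent model already contains it. They should not be counted towards the selection rule.

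**Conclusion.** The concern holds. As written, the rule makes site and illness trajectory conditional on an imbalance that stratified randomisation is designed to prevent, so they are left out in about 95% to 100% of trials, depending on blocking. It introduces no bias and does not inflate type I error. It gives a conservative test and wider intervals than necessary. The power forgone is modest: 1.4 to 5.3 points for R² of 5% to 20%, and less below that, assuming blocked allocation, a 0.30 SD effect, two-sided 0.05 and complete data.

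The primary model is also not fixed in advance, since its covariates wait on a comparison of the arms with no stated threshold. Adjustment for baseline ESAS is an open question rather than an error. If it is absent from the intended model, it is the larger of the two gains. The point is worth fixing because the remedy costs almost nothing.

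**What to change.** Replace the selection sentence in Section XI with wording such as:

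> Day 7 ESAS will be regressed on treatment group with baseline ESAS, site, race and illness trajectory as fixed covariates, whatever the observed baseline balance. Continuous secondary outcomes will be adjusted in the same way for their own baseline value. Baseline characteristics will be summarised by arm and not used to select covariates.

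The models that use Z should be rewritten so that Z is this fixed list. The levels of illness trajectory used in randomisation should be stated. Day 30 resource use has no baseline measure and needs its own stated covariate set; site, race and trajectory would be consistent with the rest. Any further demographic covariate should be named in advance on prognostic grounds. If the full models already contain a baseline term, only the site, race and trajectory part is new.

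The cost is SAP wording, with no new data. The covariates use 2 (site) + 1 (race) + 2 (trajectory, if three levels) + 1 (baseline ESAS) = 6 degrees of freedom out of 352.
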